## 6.5 Interim Analysis

An interim analysis of descriptive endpoints will be performed when all enrolled subjects either reach the 12-month visit or are discontinued from the study prior to the 12-month visit.

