#### 4.3.3 Demographic/Baseline Characteristic and Descriptive Endpoint(s)

- Change from baseline to 12, 18 and 24 months post-permanent implant for quality of life measured using the EQ5D questionnaire.
- Change from baseline to 3, 12, 18, and 24 months post-permanent implant for pain catastrophizing measured using the PCS.
- Change from baseline to 12, 18 and 24 months post-permanent implant for anxiety measured using the STAI.
- Change from baseline to 12, 18 and 24 months post-permanent implant for depression measured using the PHQ9.
- Change from baseline to 3, 12, 18 and 24 months post-permanent implant for fear avoidance measured using the TSK.
- Change from baseline to 12, 18 and 24 months post-permanent implant for sleep measured using the MOS Sleep Scale.
- Change from baseline to 12, 18 and 24 months post-permanent implant for physical function measured using the PROMIS Physical Function Scale.
- Change from baseline to End of Trial system evaluation 3, 12, 18, and 24 months post-permanent implant in pain assessed by using the NRS.
- Demographics and baseline characteristics.
- Patient waveform preference (if applicable).
- Patient satisfaction at End of Trial system evaluation 3, 6, 12, 18, and 24 months post-permanent implant.
- Global improvement of the patient by using the Patient Global Impression of Change (PGIC) at End of Trial System Evaluation 3, 6, 12, 18, and 24 months.
- Medication usage measured in decrease in chronic pain related medication intake since baseline at 3, 6, 12, 18, and 24 months post-permanent implant.
- Battery consumption and/or recharging activities.
- Stimulation Assessment measured by using the Stimulation Assessment Form at 3, 6, 12, 18, and 24 months post-permanent implant as well as any unscheduled visit where reprogramming occurs.
- Program information including amplitude, pulse width, frequency and electrode configuration.
- System information including device type, model number, serial number and number of leads.
- Proportion of device, or procedure-related Serious Adverse Events (SAE)'s and non-serious adverse events in subjects who receive permanent implant of the SCS system.

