## 6.3 Overall Sample Size

The study aims to enroll 267 subjects based on assumptions drawn from experience with the Prodigy I study. Assuming a trial failure rate of 30%, and an attrition rate of 10% between baseline and trial, and 14% from permanent implant to 6-month follow-up, 168 subjects are projected to complete the permanent implant and 145 subjects are projected to complete the 6-month follow-up for primary endpoint evaluation. One hundred forty-five (145) subjects with evaluable NRS data at baseline and 6-month visit provides a 95% confidence interval on the NRS change from baseline to 6-month with half interval width of 0.49 assuming the standard deviation of the NRS change is 3.

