## 6.4 Timing of Analysis

The analysis of primary and secondary endpoints will be conducted when 145 subjects have a permanent system implant and complete the 6-month follow-up endpoint evaluation. The final report will be conducted after all enrolled subjects either complete the 24-month visit or are discontinued from the study prior to the 24-month visit.

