## **10 Monitoring**

Centralized monitoring will occur through routine internal data review. This monitoring is designed to identify missing and inconsistent data, data outliers, and potential CIP deviations that may be indicative of site non-compliance. On-site monitoring may occur at the discretion of the Sponsor.

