## **12 Suspension or Premature Termination of the Clinical Investigation**

The Sponsor reserves the right to terminate the clinical investigation at any stage, with appropriate written notice to the Investigators, IRB/ECs and relevant Regulatory authorities, if required.

A Principal Investigator, IRB/EC or regulatory authority may suspend or prematurely terminate participation in a clinical investigation at the investigational sites for which they are responsible. The Investigators will follow the requirements specified in the Clinical Trial Agreement.

If suspicion of an unacceptable risk to subjects arises during the clinical investigation or when so instructed by the IRB/EC or regulatory authority, the Sponsor may suspend the clinical investigation while the risk is assessed. The Sponsor will terminate the clinical investigation if an unacceptable risk is confirmed. If the Sponsor completes an analysis of the reasons for the suspension, implements the necessary corrective actions, and decides to lift the temporary suspension, the Sponsor will inform the Principal Investigators, IRB/EC, or regulatory authority, where appropriate, of the rationale, providing them with the relevant data supporting this decision. Approval from the IRB/EC or regulatory authority, where appropriate, will be obtained before the clinical investigation resumes. If subjects have been informed of the suspension, the Principal Investigator or authorized designee will inform them of the reasons for resumption.

If the Sponsor suspends or prematurely terminates the clinical investigation at an individual investigational site in the interest of safety, the Sponsor will inform all other Principal Investigators.

If suspension or premature termination occurs, the Sponsor will remain responsible for providing resources to fulfill the obligations from the CIP and existing agreements for following up the subjects enrolled in the clinical investigation, and the Principal Investigator or authorized designee will promptly inform the enrolled subjects at his/her investigational site, if appropriate.

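### No adverse-event summary is scheduled with the 6-month primary analysis; the first comes about 30 to 33 months after first enrolment and leaves out subjects who fail the trial

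*Combined protocol and SAP*

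**What the plan says.** Section 4.3.3 places the plan's one safety endpoint among the demographic, baseline and descriptive items. It begins "Proportion of device, or procedure-related Serious Adverse Events", goes on to non-serious events, and is restricted to subjects who receive the permanent implant. Section 6.1.3 repeats that restriction and plans frequencies and percentages. No primary or secondary endpoint in 4.3.1 or 4.3.2 concerns safety.

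Two sections set when endpoints are analysed before the final report:
- Section 6.4: "The analysis of primary and secondary endpoints will be conducted when 145 subjects have a permanent system implant and complete the 6-month follow-up" evaluation.
- Section 6.5: "An interim analysis of descriptive endpoints will be performed when all enrolled subjects either reach the 12-month visit or are discontinued" before that visit.

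The final report follows when all subjects have completed 24 months or been discontinued (6.4).

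Safety reporting runs separately. Under section 8.2, surveillance by the investigator and the sponsor starts at consent. All serious events whatever their cause, all non-serious device- or procedure-related effects and all MRI-related events go to the sponsor within 3 calendar days of site awareness. Section 10 describes routine central data review and says of it: "This monitoring is designed to identify missing and inconsistent data, data outliers, and potential CIP deviations that may be indicative of site non-compliance". Section 12 lets the sponsor suspend the study: "If suspicion of an unacceptable risk to subjects arises during the clinical investigation". Section 6.6 sets no statistical criteria for termination.

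**The concern.** The classification of an endpoint decides when it is analysed. Because adverse events are only descriptive, they fall outside the 6-month analysis and wait for a later one whose trigger is every enrolled subject reaching 12 months or discontinuing. On the plan as written, the primary pain result would be produced with no scheduled safety summary beside it.

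The population is a second gap. Every subject who goes on to a trial undergoes a lead procedure, and reportable events are collected from consent onward. The planned table counts only those who proceed to permanent implant. Events in subjects whose trial fails would sit in the database without appearing in any planned summary, including the final one. That makes the safety account incomplete for a treatment whose first step is the trial procedure.

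**Working it through.** **The plan's own figures.** Section 6.3 states: "The study aims to enroll 267 subjects based on assumptions drawn from experience with the Prodigy I study". Its rates are a 10% loss before the trial, a 30% failure rate at the trial and a 14% loss between implant and the 6-month visit. From these it projects 168 implants and 145 completers at 6 months.
- Subjects reaching a trial: 267 × 0.90 = 240.3
- Permanent implants: 240.3 × 0.70 = 168.2 (plan: 168)
- 6-month completers: 168.2 × 0.86 = 144.7 (plan: 145)
- Half-width of the 95% interval with SD 3: 1.96 × 3/√145 = 0.488 (plan: 0.49)

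All reproduce.

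**Subjects outside the planned table.** Projected trial failures: 267 × 0.90 × 0.30 = 72.1, about 72 of the 240 who undergo a trial. They are withdrawn when the trial ends (5.3.3), so their reporting window is short, but it includes the trial procedure itself.

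**Timing inputs.** Enrolment is estimated at about 18 months (4.1). The trial follows baseline by 3 to 45 days (5.3.1, 5.3.2). Permanent implant has no fixed limit after a successful trial (5.3.4); an on-the-table trial puts both in one procedure. I therefore take a lag from enrolment to implant of 3 or 45 days, and 90 days as an assumed longer case. The 12-month visit is counted from permanent implant, ±60 days (5.3.7). With 30.4375 days to the month, the lags are 0.10, 1.48 and 2.96 months, and 60 days is 1.97 months. Months count from first enrolment.

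| Lag | Last implant (18 + lag) | 6-month visit (+ 6) | 12-month visit (+ 12) |
|---|---|---|---|
| 3 days | 18.1 | 24.1 | 30.1 |
| 45 days | 19.5 | 25.5 | 31.5 |
| 90 days (assumed) | 21.0 | 27.0 | 33.0 |

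With the visit window, the section 6.5 analysis ranges from 30.1 − 1.97 = 28.1 to 33.0 + 1.97 = 34.9. That all initial implants precede it needs no assumption, because the trigger requires every subject to be at 12 months after implant or discontinued.

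**What adding adverse events to 6.4 would gain.** On the plan's rates, the 145 completers are in effect the whole projected completer set (144.7), so the 6-month analysis falls when the last of them is seen, at about month 24 to 27. If attrition after implant is lower, the 145th completer arrives sooner. With even enrolment and a 1.5-month lag:
- 10% attrition: 168.2 × 0.90 = 151.4; 18 × 145/151.4 + 1.5 + 6 = 24.7
- No attrition: 18 × 145/168.2 + 1.5 + 6 = 23.0

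The gain is 6 months at the plan's rates (30.1 − 24.1, or 33.0 − 27.0), and 6.8 to 8.5 months with the lower attrition (31.5 − 24.7 and 31.5 − 23.0). In each case the table still follows the last implant.

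**Implants in place during enrolment.** With even enrolment and a 1.5-month lag, 168 × (12 − 1.5)/18 = 98 implants exist at month 12 and 168 × (18 − 1.5)/18 = 154 at month 18. No cumulative table is scheduled at either point.

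**The case against.** A reader might infer that the first table comes too late to inform the suspension rule in section 12. The documents do not support that. Section 12 acts on a suspicion of unacceptable risk at any time and is not tied to the section 6.5 analysis. Section 8.2 gives the sponsor as well as the investigator a surveillance duty from consent and brings reportable events to the sponsor within 3 calendar days, and they are held in a database that the sponsor hosts (9.2). Nothing prevents the sponsor from counting them when it chooses. The average of 168/30 = 5.6 implants per centre does not change this, because all centres report to one sponsor.

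A reader might also infer that moving the summary to the 6-month analysis would allow implants to be prevented. It would not: month 24 to 27 is after the last implant at about month 18 to 21.

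Three further points have force. The devices are market released and used within their instructions, and vigilance and complaint reporting run in parallel (8.2, 8.2.2). Section 6.4 fixes timing and does not forbid reporting adverse events alongside. A data management plan is referred to (9.2) and a monitoring plan is among the abbreviations; neither is in the document, so the absence of a periodic review can be shown only for the text at hand.

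These points limit the seriousness. They do not supply a scheduled summary with the primary analysis, and none of them brings the trial failures into the planned table.

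**Conclusion.** The point holds as a modest gap in safety reporting. The plan schedules no cumulative adverse-event summary with the 6-month primary analysis. The first is due at about month 30 to 33 at the nominal visit, or about 28 to 35 with visit windows, and follows all initial implants. The planned table omits about 72 projected trial failures, roughly 30% of the 240 subjects expected to undergo a trial.

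The dates rest on the plan's 18-month enrolment estimate and on an assumed lag to implant of up to 90 days. Slower enrolment would move them later. Faster enrolment, or trial failure among the last subjects enrolled, would move them earlier. The count of 72 rests on the plan's 10% and 30% rates. The number of events in those subjects cannot be estimated from the documents. Neither the primary pain estimate nor the sponsor's ability to suspend is affected.

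**What to change.** In section 6.4, add to the 6-month analysis a cumulative summary of serious adverse events and of device- or procedure-related adverse events, for all subjects who had a trial or permanent procedure by that date. Show the trial and permanent phases separately, each with its own denominator. Use the same population in section 6.1.3, and align 4.3.3 with it, so that the section 6.5 analysis and the final report are complete too.

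Optionally, add a periodic cumulative adverse-event listing to the routine central review in section 10 while enrolment is open. Only this part would give a cumulative view during the implant period; whether to add it, and how often, is for the sponsor to judge.

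The cost is plan wording and minor programming and review time, including an extension of the planned table to subjects who had only a trial. The events are already collected under section 8.2, so no new data are needed. The plan tests no hypothesis on these endpoints, so no error rate is affected.

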## 6.6 Statistical Criteria for Termination

There are no statistical criteria for terminating this clinical investigation.

## 6.7 Deviations from Statistical Plan

If any deviations from the original statistical plan occur, such deviations will be documented in the clinical study report or statistical report containing the analysis results.

# 7 Risks and Benefits

There are no additional risks of the clinical study beyond those associated with the implant and use of the CE/FDA-approved trial and permanent neurostimulation systems. Please refer to section 7.1.1 for the list of anticipated adverse events.

## 7.1 Risks Associated with the Clinical Study Device

### 7.1.1 Anticipated Adverse Device Effects

The use of a neurostimulation system involves risks. In addition to the risks commonly associated with surgery, below are listed the anticipated potential adverse effects with the use of a neurostimulation system:

- Unpleasant sensations or motor disturbances, including involuntary movement, caused by stimulation at high outputs (if either occurs, turn off your EPG/IPG immediately)
- Undesirable changes in stimulation, which may be related to cellular changes in tissue around the electrodes, or changes in electrode position
- Changes in stimulation or reduced pain relief due to loose electrical connections

- Changes in stimulation or reduced pain relief due to lead failure
- Stimulation in unwanted places or chest wall stimulation
- Changes in stimulation or reduced pain relief due to lead migration
- Epidural hemorrhage
- Hematoma
- Infection
- Spinal cord compression
- Paralysis from placement of a lead in the epidural space
- Cerebrospinal fluid (CSF) leakage
- Paralysis below the level of implant
- Weakness, clumsiness and numbness below the level of implant
- Pain below the level of implant
- Persistent pain at the lead site
- Persistent pain at the IPG site
- Seroma (mass or swelling) at the IPG site
- Seroma at the lead incision site
- Allergic or rejection response to device/implant materials
- Implant migration
- Skin erosion around the implant
- Loss of stimulation due to premature battery depletion/battery failure

The St. Jude Medical™ MRI conditional neurostimulation systems are designed to minimize the potential adverse events that may cause patient harm. The following potential adverse events may occur in the MRI environment:

- Lead electrode heating resulting in tissue damage or serious patient injury
- IPG heating resulting in tissue damage in the implant pocket or patient discomfort or both
- Induced currents on leads resulting in overstimulation or shocking sensations
- Damage to the IPG or leads causing the system to fail to deliver stimulation or causing the system to deliver overstimulation
- Damage to the functionality or mechanical integrity of the IPG resulting in the inability to communicate with the IPG
- Movement or vibration of the IPG or leads

### 7.1.2 Risks Associated with Clinical Investigation Assessments

#### 7.1.2.1 *Residual Risks Associated with the devices in this study, as identified in the risk analysis report*

The clinical risks associated with neurostimulation systems are well known. Any potential residual risks are considered to be outweighed by the benefits, and the overall residual risk was determined to be acceptable. Clinical evidence demonstrates acceptable safety and performance of the device under this post-market study.

#### 7.1.2.2 *Risks Associated with participation in the clinical study*

The risks involved with this study are comparable to those associated with the implant of any other commercially available neurostimulation system.

#### **7.1.2.3 Possible Interactions with Concomitant Medical Treatments and/or concurrent medical interventions**

Please refer to the Clinician's Manual for information related to MRI compatibility and any possible interactions with concomitant medical treatment.

#### **7.1.2.4 Steps that will be taken to control or mitigate the risks**

The Sponsor will employ measures throughout the course of this study to minimize these risks (e.g. clearly defined inclusion and exclusion criteria to ensure that only appropriate subjects are enrolled, proper consenting process, selection of investigational sites that have a sufficient level of clinical expertise, Investigator selection, appropriate training for all involved in the study activities etc.).

### **7.2 Anticipated Benefits**

The information collected in this clinical study will be added to the current knowledge and understanding of treatment options for patients requiring a SCS treatment.

### **7.3 Risk-to-Benefit Rationale**

Any undesirable side effects, under normal conditions of use, are considered acceptable risks when weighed against the performance of the device and benefits to the subject.

## **8 Requirements for Investigator Records and Reports**

### **8.1 Deviations from CIP**

A deviation is defined as an instance(s) of failure to follow, intentionally or unintentionally, the requirements of the CIP. The Investigator should not deviate from the CIP.

In some cases, failure to comply with the CIP may be considered failure to protect the rights, safety and well-being of subjects; such non-compliance exposes subjects to unreasonable risks. Examples: failure to adhere to the inclusion/exclusion criteria, failure to perform safety assessments intended to detect adverse events. Investigators should seek to minimize such risks by adhering to the CIP.

The PI must maintain accurate, complete, and current records, including documents showing the date of and reason for each deviation from the CIP. Relevant information for each deviation will be documented as soon as possible on the applicable CRF. The site will submit the CRF to the Sponsor.

The PI is required to adhere to local regulatory requirements for reporting deviations to IRB/EC.

Under emergency circumstances, deviations from the CIP to protect the rights, safety and well-being of subjects may proceed without prior approval of the Sponsor and the IRB/EC. Such deviations shall be documented and reported to the Sponsor and the IRB/EC as soon as possible.

### **8.2 Safety Reporting**

Safety surveillance within this study and the safety reporting both performed by the Investigator and the Sponsor, starts as soon as the subject is enrolled in this study (date of signature of the informed consent).

## Clinical Investigation Plan

Safety surveillance and the safety reporting will continue until the last investigational visit has been performed, the subject is deceased, the subject/Investigator concludes his participation into the clinical investigation or the subject withdrawal from the clinical investigation.

All adverse event data including deaths will be collected throughout the clinical investigation and will be reported to the Sponsor on a CRF.

Adverse events will be monitored by the Investigator until they are adequately resolved or the subject has ended his/her participation in the trial, whichever comes first. The status of the subject's condition should be documented and reported to the Sponsor at each visit.

Per the CIP, the applicable reportable adverse event data including deaths will be collected throughout the clinical study and will be reported to the Sponsor through the EDC system. The Sponsor will ensure that all applicable events are reported to the relevant authorities as per regulations. The Investigator must notify the IRB/EC, if appropriate, in accordance with national and local laws and regulations, of the AEs reported to the Sponsor.

Reportable events to Sponsor are considered:

- All non-Serious Adverse Device Effects (procedure/device related)
- All Serious Adverse Events (whether or not the event is considered device or procedure related)
- Adverse events related to MRI scan

All the above events will be reported to the Sponsor, as soon as possible, but no later than 3 calendar days from the day the site personnel became aware of the event, or as per the investigative site's local requirements if that requirement is more stringent. The date the site staff became aware that the event met the criteria for an SAE must be recorded in the source documents.

For unexpected failure modes or unexpected adverse events, the site should follow their standard reporting practices for medical device reporting (MDR)/Vigilance reporting for medical devices per the regulations.

### **8.2.1 Subject Death**

Subject deaths will be documented and reported to the Sponsor on the applicable CRF as soon as possible after becoming aware of the event. It is the Investigator's responsibility to notify the IRB/EC per the IRB/EC policy.

Should death occur, the Investigator is requested to record death information in the hospital records and immediately document the information on the Death CRF and submit to Sponsor through the electronic data capture (EDC) system deployed by Abbott.

- All efforts to obtain the details about the circumstances surrounding the patient death should be made by the Investigator.
- If a death event is an outcome of an adverse event, an AE CRF must be completed in addition to the Death CRF.
- The subject's death is an early conclusion of the subject's participation in the study. Therefore, the Investigator is requested to complete the Withdrawal form.

